| Weeks**** | | -4 | 0 | 2 | 6 | 12 | as needed | 24 | 26 | as needed | 36 | as needed | 52 | as needed | 52 plus Q12w | as needed | | |
| Days**** Time window for visits (days) | Before or at the latest at Visit 1 | ≤28d before Visit 2 | D 1**** none | 15 ±3 | 43 ±3 | 85 ±3 | na | 169 ±3 | 183 ±3 | na | 253 ±7 | na | 365 ±7 | na | 365 plus Q84d ±7 | na | | EoT plus 28 days +3 |
| Weight ⁴ | | X | X | X | X | X | | X | | | X | | X | | X | | X | (X) |
| 12 lead-ECG (at rest) ⁵ | | X | (X) | | | | | X | | | | | X | | X /Q24w | | X | |
| Laboratory tests ^{6,7,8} | | X ⁷ | X | X | X | X | (X) | X | X | (X) | X | (X) | X | (X) | X | (X) | X | (X) |
| Pregnancy tests ⁹ | | X | X | X | X | X | | X | X | | X | | X | | X | | X | X |
| Review with patient and dispense pregnancy test diary card together with urine dipstick pregnancy test (if applicable) ⁹ | | | | | X | X | | X | X | | X | | X | | X | | X | |
| | | | | | | | | | | | | | | | | | | |
| SpO ₂ (room air, resting) | | X | X | X | X | X | | X | X | | X | | X | | X | | X | |
| FVC ¹¹ | | X | X | X | X | X | | X | X | | X | | X | | X | | X | |
| DLCO ¹¹ | | | X | | | | | | | | | | | | | | | |
| Fan severity score | | | X | | | | | | | | | | | | | | | |
| Review of in-/exclusion criteria | | X | X | | | | | | | | | | | | | | | |

| Trial Periods | Screening | | Treatment* | | | | | | | | | | | | | | | Follow-up |
|---|------------------------------------|---------------------|-------------------|----------|----------|----------|-----------|-----------------|-------------------|-----------|-----------|-----------|-----------|-----------|------------------|-----------|-------|---------------------|
| | | | Randomised Part A | | | | | | Open label Part B | | | | | | | | | |
| Visit | | 1 | 2 | 3 | 4 | 5 | 5a | 6 | 7 | 7a | 8 | 8a | 9 | 9a | X | Xa | EoT** | EoTrial*** |
| Weeks**** | | -4 | 0 | 2 | 6 | 12 | as needed | 24 | 26 | as needed | 36 | as needed | 52 | as needed | 52 plus Q12w | as needed | | |
| Days**** Time window for visits (days) | Before or at the latest at Visit 1 | ≤28d before Visit 2 | D 1**** none | 15 ±3 | 43 ±3 | 85 ±3 | na | 169 ±3 | 183 ±3 | na | 253 ±7 | na | 365 ±7 | na | 365 plus Q84d ±7 | na | | EoT plus 28 days +3 |
| IRT call/ notification | X ¹² | | X | X | X | X | | X ¹² | | | X | | X | | X | | X | |
| Randomisation | | | X | | | | | | | | | | | | | | | |
| Administer trial drug | | | X | X | | | | X | X | | | | | | | | | |

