| Dispense PK diary card ¹³ | | | X | | | | | X | | | | | | | | | | |
| PK Sampling ¹³ | | | | X | | | | | X | | | | | | | | | |
| Dispense trial drug | | | X | X | X | X | | X | | | X | | X | | X | | | |
| Collect trial drugs | | | | X | X | X | | X | | | X | | X | | X | | X | |
| Compliance check/ drug accountability | | | | X | X | X | | X | X ¹⁴ | | X | | X | | X | | X | |
| Criteria for dose reduction/ interruption check | | | | X | X | X | | X | X | | X | | X | | X | | X | |
| Acceptability questionnaire | | | | X | | | | X | | | | | | | | | | |
| PedsQL ^{TM15} | | | X | | | | | X | | | | | X | | | | | |
| 6MWT, Borg CR-10 scale®, SpO ₂ | | | X | | | | | X | | | | | X | | | | | |

| Trial Periods | Screening | | Treatment* | | | | | | | | | | | | | | | Follow-up |
|--|------------------------------------|---------------------|-------------------|----------|----------|----------|-----------|-----------|-------------------|-----------|-----------|-----------|-----------|-----------|------------------|-----------|-------|---------------------|
| | | | Randomised Part A | | | | | | Open label Part B | | | | | | | | | |
| Visit | | 1 | 2 | 3 | 4 | 5 | 5a | 6 | 7 | 7a | 8 | 8a | 9 | 9a | X | Xa | EoT** | EoTrial*** |
| Weeks**** | | -4 | 0 | 2 | 6 | 12 | as needed | 24 | 26 | as needed | 36 | as needed | 52 | as needed | 52 plus Q12w | as needed | | |
| Days**** Time window for visits (days) | Before or at the latest at Visit 1 | ≤28d before Visit 2 | D 1**** none | 15 ±3 | 43 ±3 | 85 ±3 | na | 169 ±3 | 183 ±3 | na | 253 ±7 | na | 365 ±7 | na | 365 plus Q84d ±7 | na | | EoT plus 28 days +3 |
| ILD exacerbations | | | X | X | X | X | | X | X | | X | | X | | X | | X | X |
| Hospitalizations (respiratory-related) | | | X | X | X | X | | X | X | | X | | X | | X | | X | X |
| Bone imaging (if applicable) ¹⁶ | | | X | | | X | | X | | | X | | X | | X /Q24w | | X | |
| Dental examination ¹⁶ | | | X | | | X | | X | | | X | | X | | X /Q24w | | X | |
| Dental imaging ¹⁶ | | | X | | | | | X | | | | | X | | X /Q48w | | X | |
| All AEs/SAEs/AESIs ¹⁷ | X | X | X | X | X | X | | X | X | | X | | X | | X | | X | X |
| Concomitant therapy | | X | X | X | X | X | | X | X | | X | | X | | X | | X | X |
| Completion of patient participation | | | | | | | | | | | | | | | | | | X |
| Vital status data ¹⁸ | | | | | | | | X | | | | | X | | | | | X |

- (*) In case of dose change (reduction or re-escalation) additional visits have to be included.

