- (**) Patients who discontinue trial treatment prematurely should undergo the End of Treatment (EoT) visit as soon as possible, and follow the trial schedule thereafter, if possible. The patient will be asked to attend all visits (except for the laboratory a-visits) as originally planned until the end of the trial. Please also see Flow Chart footnote 18 for instructions, should the patient be unable to complete the scheduled visits; see [Section 6.2.3](#) for details on trial procedures at these visits. The first visit after the EoT visit will be skipped if the EoT visit occurs within 4 weeks prior to scheduled visit. Patients who did not discontinue trial treatment prematurely should undergo the EoT visit as soon as the timing of final DBL (DBL 2) and EoT visit has been communicated (see [Section 3.1](#) for details). If a regular study visit is scheduled in the period when the EoT visit should be conducted, all procedures required at this regular study visit and the additional procedures, if any, required at the EoT visit will be conducted during the same visit.
- (***) After the EoT visit, patients who completed the treatment period according to protocol will enter a 4-week follow-up period, unless they roll-over into an open label extension trial. See [Section 3.1](#) for details.
- (****) Weeks and Days from the Day of Randomisation, i.e. Day of first intake of randomised medication (D 1).

¹Informed consent (and assent where applicable) will be obtained before any procedure related to the study. When it is obtained before Visit 1, e.g. to allow shipment of images for central review, all Adverse Events (AEs) and Concomitant Treatments occurring after the informed consent have to be recorded, including those occurred between informed consent and Visit 1. The interval between Visit 1 and Visit 2 should be ≤ 28 days. The interval between Visit 1 and Visit 2 could be >28 days in case the assessments required to check inclusion and exclusion criteria cannot be completed within 28 days (e.g. in case the available HRCT scan fails to meet the required image acquisition specification, laboratory test results show out-of-range values requiring retest, etc.) but the screening period (informed consent to Visit 2) must not be longer than 12 weeks. Upon obtaining informed consent, the patient and parent(s)/legal guardian will be instructed on procedures to be followed until the next study visit.

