- The patient can no longer receive trial treatment for medical reasons (such as adverse events, other diseases, or pregnancy).

If a patient becomes pregnant during the trial the investigational product must be discontinued immediately, and the patient will be followed up until birth or otherwise termination of the pregnancy. The data of the patient will be collected and reported in the clinical trial report (CTR) until patient's last visit, and any events thereafter will be reported in the Boehringer Ingelheim (BI) drug safety database. Refer to [Section 5.2.7.2.3](#) for detailed information on event reporting in case of pregnancy.

In case of discontinuation of trial medication, it is of utmost importance for the robustness and integrity of the trial results that the patient remains in the study and returns to all

regularly scheduled visits until the end of the trial. For those patients who are unable to complete the scheduled visits, every attempt will be made to get information on vital status at 24 weeks after randomization, i.e. the time of the data cut-off for the primary analysis, at 52 weeks after randomization and at the end of the trial, as outlined in the [Flow Chart](#) and [Section 6.2.3](#).

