- Visit 6 only: a PK diary card will be dispensed; the patient and parent(s)/legal guardian will be instructed on how it should be completed in the 3 days before the next visit. If PK sampling needs to be repeated (see [Flow Chart for PK blood sampling](#) and [Section 5.3.1](#) for details), the PK diary card will be dispensed during the visit before PK sampling, and the patient will be instructed as needed.
- Urine dipstick pregnancy tests and a pregnancy test diary card will be dispensed (females only); the patient and parent(s)/legal guardian will be instructed on how the test should be conducted, and the diary should be completed, until the next visit.
- The next visit will be scheduled; patient and parent(s)/legal guardian will be instructed on procedures to be followed until the next visit. In preparation to Visit 6 the patient and parent(s)/legal guardian will be instructed that on the day of this visit the morning dose of trial medication should not be taken before going to the site, because the morning dose will be taken during the visit.
- Follow-up MRIs (or x-rays if baseline MRI was not possible) of epiphyseal growth plates will be conducted* - in patients with open physes only - at 12 weeks, 24 weeks, 36 weeks, 52 weeks and every 24 weeks thereafter, until the end of the study or closure of the physes. MRIs (or x-rays) will be sent to central evaluation by radiology expert on a timely manner.
- Follow-up dental examination will be conducted* in all patients at 12 weeks, 24 weeks, 36 weeks, 52 weeks and every 24 weeks thereafter until the end of the study.
- Follow-up dental imaging will be conducted* in all patients at 24 weeks, 52 weeks and every 48 weeks thereafter until the end of the study. Panoramic x-ray will be sent to central evaluation by paediatric dentistry expert on a timely manner.

*If it's not possible to conduct this procedure on the day of the visit, the procedure can be done in the week immediately before or after the visit (please refer to the image acquisition guideline available in the ISF for details).

End of Treatment Visit

Patients who discontinue trial treatment prematurely will undergo the End of Treatment (EoT) visit as soon as possible, and complete procedures defined (see [Flow Chart](#) and [Section 3.3.4](#)). The first visit after the EoT visit will be skipped if the EoT visit occurs within 4 weeks prior to the scheduled visit.

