During these visits the patient will undergo the following observations and procedures:

- PedsQL™ questionnaire will be administered prior to any other procedures and checked for completeness (Visit 6 and Visit 9 only).
- Adverse events, any ILD exacerbations, respiratory-related hospitalizations [REDACTED] and concomitant therapy since last visit will be reviewed and recorded.
- Physical examination including vital signs, weight, height, and leg length will be performed (height and leg length not planned at Visit 4; leg length planned every 24 weeks after the first year); data will be recorded in source documents and timely transferred per instructions provided (see ISF), to ensure central review as needed.
- SpO₂ measurement will be conducted on room air at rest.
- FVC measurement will be conducted according to procedures defined (see ISF for details).
- The 6-minute walk test including Borg CR-10 scale® and continuous pulse oximetry (SpO₂) will be conducted (Visit 6 and Visit 9 only).

- The next visit will be scheduled; patient and parent(s)/legal guardian will be instructed on procedures to be followed until the next visit.
- Follow-up MRIs (or x-rays if baseline MRI was not possible) of epiphyseal growth plates will be conducted* - in patients with open physes only - at 12 weeks, 24 weeks, 36 weeks, 52 weeks and every 24 weeks thereafter, until the end of the study or closure of the physes. MRIs (or x-rays) will be sent to central evaluation by radiology expert on a timely manner.
- Follow-up dental examination will be conducted* in all patients at 12 weeks, 24 weeks, 36 weeks, 52 weeks and every 24 weeks thereafter until the end of the study.
- Follow-up dental imaging will be conducted* in all patients at 24 weeks, 52 weeks and every 48 weeks thereafter until the end of the study. Panoramic x-ray will be sent to central evaluation by paediatric dentistry expert on a timely manner.

*If it's not possible to conduct this procedure on the day of the visit, the procedure can be done in the week immediately before or after the visit (please refer to the image acquisition guideline available in the ISF for details).

These visits will be regarded as part of the trial despite the patient having discontinued trial medication.

The need for coming to future visits in case of prematurely discontinuation of trial medication will be explained to patients and parent(s)/legal guardian prior to start of trial participation.

[figure not shown]

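### An End of Treatment visit held in the 4 weeks before Visit 6 or Visit 9 cancels that visit but includes neither PedsQL nor the 6-minute walk test, so a few early stoppers lose the week-24 or week-52 value by rule

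*Protocol*

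**What the plan says.** **Skip rule.** Flow Chart footnote (**) asks patients who discontinue early to have an EoT visit promptly and then to follow the schedule, with one exception: "The first visit after the EoT visit will be skipped if the EoT visit occurs within 4 weeks prior to scheduled visit". Section 6.2.2 (End of Treatment Visit) repeats this in its paragraph on early discontinuation: "The first visit after the EoT visit will be skipped if the EoT visit occurs within 4 weeks prior to the scheduled visit".

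**Schedule of the two tests.** The Flow Chart rows are "PedsQL ^{TM15} | | | X | | | | | X | | | | | X" and "6MWT, Borg CR-10 scale®, SpO ₂ | | | X | | | | | X | | | | | X". The three marks stand under Visits 2, 6 and 9, and the EoT cell is empty in both rows. Section 6.2.2 refers back to the Flow Chart for the EoT procedures and adds neither test.

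**Patients off drug.** Section 6.2.3 keeps the same limit at later visits: "PedsQL™ questionnaire will be administered prior to any other procedures and checked for completeness (Visit 6 and Visit 9 only"), and for the walk test "continuous pulse oximetry (SpO₂) will be conducted (Visit 6 and Visit 9 only").

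**Endpoints and aim.** Protocol Section 2.1.3 lists the change in PedsQL and in 6-minute walk distance at weeks 24 and 52 as secondary endpoints. Section 3.3.4.1 says of patients who stop drug that "it is of utmost importance for the robustness and integrity of the trial results that the patient remains in the study" and attends the scheduled visits.

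**The concern.** The skip rule assumes that the EoT visit can stand in for the scheduled visit that it displaces. For FVC and resting SpO2 it can, because both are marked at EoT. For PedsQL and the 6MWT it cannot. The rule removes the only visit in that period at which they are due, and nothing moves them to the visit that is held.

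The gap falls only on children who have stopped drug. The SAP analyses the continuous secondary endpoints by randomised treatment with data from all visits (Section 7.5.2.1) and treats missing values as missing at random (Section 6.6.2.1), so off-drug values are wanted. Unlike FVC, these two endpoints have no scheduled post-baseline measurement before Visit 6.

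**Working it through.** The plan states no figure for this point, so there is none to reproduce. The check is visit-day arithmetic, then a rough count.

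**1. Inputs**
- Planned days, from the Flow Chart row for Visits 5 to 9: "85 ±3 | na | 169 ±3 | 183 ±3 | na | 253 ±7 | na | 365 ±7". Visit 5 is day 85, Visit 6 day 169, Visit 8 day 253 and Visit 9 day 365.
- Skip span: 4 weeks = 28 days.
- SAP Table 6.7: 6 windows for PedsQL and 6MWT: week 24 = days 2 to 267; week 52 = days 268 to 463.
- At least 30 randomised, 2:1 (Protocol synopsis).
- Share stopping in Part A: not given. Assumed 10%, 20% or 30%.
- Timing of stops: not given. Assumed even over the 168 days of Part A.

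**2. EoT dates that trigger the skip** (planned day − 28 to planned day − 1)
- Visit 6: 169 − 28 = 141 to 169 − 1 = 168. The preceding scheduled visit is on day 85, so Visit 6 is the first visit after such an EoT.
- Visit 9: 365 − 28 = 337 to 365 − 1 = 364. The preceding scheduled visit is on day 253, so Visit 9 is the first visit after.

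These days are approximate, because visits have windows of ±3 and ±7 days.

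**3. What is measured in those spans**

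| Assessment | Marked at EoT? | Value if Visit 6 or 9 is skipped |
|---|---|---|
| FVC | yes | collected at EoT |
| Resting SpO2 | yes | collected at EoT |
| PedsQL | no | not collected |
| 6MWT | no | not collected |

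**4. Other values available to the model**
- Visit 6 skipped: the only scheduled earlier value is baseline and the next is Visit 9, so there is no post-baseline value until week 52.
- Visit 9 skipped: the week-24 value from Visit 6 normally exists.

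**5. Rough count at week 24**
- Share of Part A in the span: 28/168 = 0.167.
- Expected number = 30 × share stopping × 28/168.
- Chance of at least one = 1 − (1 − share stopping × 28/168)^30.

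| Share stopping (assumed) | Expected number | Chance of at least one |
|---|---|---|
| 10% | 0.5 | 0.40 |
| 20% | 1.0 | 0.64 |
| 30% | 1.5 | 0.79 |

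For stops between weeks 24 and 52, the same reasoning puts 28/196 = 0.143 of them in the Visit 9 span. I give no count there, because the documents do not say how many will stop in that period or how many will reach week 52.

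**6. Would a value taken at EoT be usable?** Days 141 to 168 lie inside days 2 to 267, and days 337 to 364 lie inside days 268 to 463. Both would be allocated to the intended week.

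**The case against.** **The combined-visit sentence may cover this.** Footnote (**) ends with a sentence that merges a regular visit and the EoT visit when they fall in the same period, and within the footnote it is not expressly limited to completers. That is fair: the limit to completers is clear only from its place in Section 6.2.2, in the paragraph on patients who did not stop early. But even a generous reading helps only when the two visits nearly coincide, which leaves most of the 28 days uncovered.

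**The count is probably too high.** Section 1.2 places most hepatic events in the first three months, and Section 3.2 regards three months as enough to assess the most frequent adverse events. If stops come early, fewer than 1 in 6 fall in the span. This stands.

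**The consequence is limited.** No confirmatory testing is planned (Section 7.1), the secondary analyses are descriptive (Section 7.2.3), and the primary endpoints (exposure and treatment-emergent adverse events) are untouched. This also stands.

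**The model can cope.** A reader might infer that the missing-at-random model has nothing to use for these children. That is not so after a Visit 9 skip. After a Visit 6 skip it holds only until week 52 is observed, and SAP Section 7 repeats all analyses after the second database lock. SAP Section 6.6.2.3 also imputes PedsQL at week 24, but only for binary endpoints. What is lost is the observed value.

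**Nothing forbids an unscheduled test.** True, and the SAP window would accept it, but nothing asks for one.

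**Conclusion.** The gap is real but narrow. By the protocol's own rule, an early stopper whose EoT visit falls on about days 141 to 168, or 337 to 364, does not give the week-24 or week-52 value for PedsQL and 6MWT. This works against the follow-up aim in Section 3.3.4.1. On the two assumptions above, about 0.5 to 1.5 of 30 children are affected at week 24, and probably fewer.

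Three stronger readings are not supported:
- **That all early stoppers lose these values.** Only those with an EoT visit in the two spans do.
- **That the date of the last dose decides.** The trigger is the date of the EoT visit. The two should be close, because that visit is to follow promptly, but an EoT visit held on or after the planned day of Visit 6 does not cancel Visit 6.
- **That a tenth of the placebo arm is at stake.** One child would be 10% of about 10 on placebo, but with 2:1 allocation and equal stopping the expected placebo loss is a third of 0.5 to 1.5, or about 0.17 to 0.5 children.

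The case for acting is that the loss is systematic and almost free to prevent, not that it is large.

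**What to change.** In Flow Chart footnote (**), Section 6.2.2 and Section 6.2.3, add that when the EoT visit replaces Visit 6 or Visit 9, the PedsQL (completed first) and the 6MWT with Borg scale and SpO2 due at that visit are done at the EoT visit. SAP Table 6.7: 6 needs no change.

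The cost is one sentence in each place and a slightly longer EoT visit for the few children concerned. The tests move from the cancelled visit, so none is added to the planned total.

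Exempting Visits 6 and 9 from the skip rule would not be an equal alternative. It would bring back a full visit within 4 weeks of EoT and repeat measurements just taken, whereas Table 1.4.2:1 aims to keep site visits to a minimum.

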| chILD | Childhood Interstitial Lung Disease |
| cHP | Chronic Hypersensitivity Pneumonitis |
| CL/F _{ss} | Apparent Clearance of the Analyte in the Plasma at Steady-State following extravascular multiple dose administration |
| CK | Creatine Kinase |
| C _{max} | Maximum Concentration in Plasma |
| C _{max,ss} | Maximum Measured Concentration of the Analyte in Plasma at Steady State |
| CNS | Central Nervous System |
| COHb | Carboxyhaemoglobin |
| COVID-19 | Coronavirus Disease 2019 |
| C _{pre,ss} | Predose Concentration of the Analyte in Plasma at Steady State immediately before administration of the next dose |
| CRA | Clinical Research Associate |

| | |
|------------|---|
| CRF | Case Report Form, paper or electronic (sometimes referred to as “eCRF”) |
| CRA | Contract Research Associate |
| CRO | Contract Research Organisation |
| CSF1R | Colony-Stimulating Factor 1 Receptor |
| CTCAE | Common Terminology Criteria for Adverse Events |
| CT Leader | Clinical Trial Leader |
| CT Manager | Clinical Trial Manager |
| CTP | Clinical Trial Protocol |
| CTR | Clinical Trial Report |
| CV | Coefficient of Variation |
| CYP3A4 | Cytochrome P450 3A4 |
| Δ | Delta, i.e. difference |
| d | Day(s) |
| DBL | Database Lock |
| DILI | Drug Induced Liver Injury |
| DLCO | Diffusing Capacity of the Lung for Carbon Monoxide |
| DM | Dermatomyositis |
| DRC | Disease Review Committee |
| EC | Ethics Committee |
| ECG | Electrocardiogram |
| eCRF | Electronic Case Report Form |
| eDC | Electronic Data Capture |
| EDTA | Ethylenediamine-Tetraacetic Acid |
| EoT | End of Treatment |
| EoTrial | End of Trial |
| EudraCT | European Clinical Trials Database |
| FC | Flow Chart |
| FDA | Food and Drug Administration |
| FGFR | Fibroblast Growth Factor Receptor |
| FPE | First Patient Enrolled |
| FPI | First Patient In |
| FUP | Follow-up |
| FVC | Forced Vital Capacity |

| | |
|---|---|
| GCP | Good Clinical Practice |
| gCV | Geometric Coefficient of Variation |
| GFR | Glomerular Filtration Rate |
| GGT | Gamma-Glutamyl Transferase |
| GI | Gastro-Intestinal |
| GLI | Global Lung Initiative |
| GMP | Good Manufacturing Practice |
| h | hour |
| HA | Health Authority |
|  | |
| Hb | Haemoglobin |
| Hct | Haematocrit |
| HP | Hypersensitivity Pneumonitis |
| HRCT | High-Resolution Computed Tomography |
| HSCT | Haematopoietic Stem Cell Transplant |
| i.v. | intravenous |
| IB | Investigator's Brochure |
| ICH | International Conference on Harmonisation |
| IEC | Independent Ethics Committee |
| ILD | Interstitial Lung Disease |
| IMP | Investigational Medicinal Product |
| INR | International Normalized Ratio |
| IPD | Important Protocol Deviation |
| IPF | Idiopathic Pulmonary Fibrosis |
| IQRMP | Integrated Quality and Risk Management Plan |
| IRB | Institutional Review Board |
| IRT | Interactive Response Technology |
| ISF | Investigator Site File |
| IUD | Intrauterine Device |
| IUS | Intrauterine Hormone-Releasing System |
| Lck | Lymphocyte-specific Tyrosine-protein Kinase |
| LDH | Lactate Dehydrogenase |
| LFT | Liver Function Test |

| | |
|---------|---|
| LPI | Last Patient In |
| LPLT | Last Patient Last Treatment |
| LPLVPE | Last-Patient-Last-Visit-Primary-Endpoint |
| Lyn | Tyrosine-protein Kinase Lyn |
| MACE | Major Adverse Cardiovascular Events |
| MCTD | Mixed Connective Tissue Disease |
| MedDRA | Medical Dictionary for Drug Regulatory Activities |
| MMRM | Mixed Model with Repeated Measurements |
| MRI | Magnetic Resonance Imaging |
| n.a. | Not Applicable |
| NOA | Not Analysed |
| NOP | No Peak Detectable |
| NOR | No Valid Result |
| NOS | No Sample |
| NSIP | Non-Specific Interstitial Pneumonia |
| OPU | Operative Unit |
| PAH | Pulmonary Arterial Hypertension |
| PBMC | Peripheral Blood Monocytic Cells |
| PD | Pharmacodynamic(s) |
| PDGFR | Platelet-Derived Growth Factor Receptor |
| PedsQL™ | Pediatric Quality of Life Questionnaire™ |
| per os | Oral |
| PF-ILD | Progressive Fibrosing Interstitial Lung Disease |
| P-gp | Permeability Glycoprotein |
| PIP | Paediatric Investigation Plan |
| PK | Pharmacokinetic(s) |
| PKS | Pharmacokinetic Set |
| PM | Polymyositis |
| PopPK | Population Pharmacokinetics |
| PT | Prothrombin Time |
| PTM | Planned Time |
| Q | Quaque, i.e. every |
| RA | Regulatory Authority |

| | |
|---------------------|---|
| RA-ILD | Rheumatoid Arthritis associated ILD |
| RBC | Red Blood Count |
| REP | Residual Effect Period |
| s.c. | subcutaneous |
| SAE | Serious Adverse Event |
| SAP | Statistical Analysis Plan |
| SFTPC | Surfactant Protein Deficiency |
| SI | International System of units |
| SMC | Safety Monitoring Committee |
| SMQ | Standard MedDRA Query |
| 6MWT | Six-Minute Walk Test |
| SARS-CoV2 | Severe Acute Respiratory Syndrome Coronavirus 2 |
| SOC | Standard of Care |
| SOP | Standard Operating Procedure |
| SpO ₂ | Oxygen Saturation |
| Src | Proto-oncogene Tyrosine-protein Kinase |
| SSc-ILD | Systemic Sclerosis associated ILD |
| SUSARs | Suspected Unexpected Serious Adverse Reactions |
| t _{1/2,ss} | Terminal Half-life of the Analyte in Plasma at Steady State |
| t _{max,ss} | Time from Dosing to Maximum Measured Concentration of the Analyte in Plasma at Steady State |
| TKI | Tyrosine Kinase Inhibitor |
| TMF | Trial Master File |
| TS | Treated Set |
| TSAP | Trial Statistical Analysis Plan |
| UIP | Usual Interstitial Pneumonia |
| ULN | Upper Level of Normal |
| US | United States |
| VEGFR | Vascular Endothelial Growth Factor receptor |
| w | Week(s) |

WHO World Health Organisation

WOCBP Woman of childbearing potential

V_z/F_{ss}

Apparent Volume of Distribution during the Terminal Phase λ_z at Steady State following extravascular administration

